abortion is used first to completely expel the pregnancy tissue, subsequent curettage can be avoided. Regarding the use of estrogen therapy in combination with medical abortion, studies have shown that estrogen can significantly stimulate the proliferation and differentiation of endometrial stem cells, and this effect is dose-dependent. Physiological doses of estrogen promote the differentiation of endometrial stem cells and maintain the existing thickness of the endometrium; supraphysiological doses of estrogen can promote the proliferation of endometrial stem cells and promote the thickening of the endometrium. [8]. Other reports indicate that mifepristone can reduce chorionic villus activity by decreasing the content of estrogen and progesterone receptors in the decidual tissue. This leads to a decrease in estrogen receptor levels in the early pregnancy decidua, preventing estrogen from exerting its biological effects, affecting the repair of the endometrial wound after medical abortion, and causing a decrease in the sensitivity of uterine smooth muscle to oxytocin, preventing the decidua from being easily expelled and thus leaving residues in the uterine cavity. Conventional doses of exogenous estrogen often fail to restore the endometrium to an ideal state after medical abortion. Therefore, combining medical abortion with high-dose estrogen may improve the effectiveness of medical induction, reduce vaginal bleeding, and promote endometrial repair. However, in current clinical practice, there is still a lack of clinical efficacy studies on the application of high-dose estrogen in the treatment of missed abortion in early pregnancy. This study aims to evaluate the efficacy of different treatment methods for missed abortion in early pregnancy and further explore whether the treatment regimen of mifepristone combined with misoprostol and high-dose estrogen can achieve ideal efficacy and reduce the occurrence of complications, providing a valid basis for the subsequent clinical treatment of missed abortion.

2. Research Objectives

Currently, there is no unified standard for the treatment of missed abortion in clinical practice. This study aims to collect clinical data on this type of disease to compare the differences in efficacy of different treatments. Based on this, it will also explore the synergistic effect of combining different doses of estrogen with medical induction of

[figure not shown]

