labor, conduct statistical analysis on the efficacy, and evaluate whether the treatment plan achieves the desired therapeutic effect while reducing the occurrence of complications, thus providing a valid basis for the subsequent clinical treatment of missed abortion.

3. Research Design

Sample size calculation: Retrospective study of 400 cases

A prospective study of 180 cases

flow chart:

4. Research Content

This study is divided into two parts. The first part is a retrospective analysis to explore the differences in efficacy and fertility outcomes among patients with different treatment methods for missed abortion; the second part is a prospective study to explore the impact of different doses of estrogen combined with different treatment methods on the efficacy of treatment for missed abortion in early pregnancy.

Part I retrospective analysis collected data from patients with early pregnancy loss due to miscarriage who visited the Department of Gynecology at Xiangya Third Hospital of Central South University between January 2018 and March 2023. All patients had voluntarily accepted drug or surgical treatment and signed relevant treatment consent forms, and were exempted from signing informed consent forms regarding the data collection.

Part II, a prospective study, collected data from patients with early pregnancy loss due to miscarriage who visited the Department of Gynecology at Xiangya Third Hospital of Central South University between December 2023 and December 2024. All patients received either medication or surgical treatment at their own discretion. All participants were required to provide fully informed consent and sign an informed consent form.

Selection criteria:

① Age 18-40 years ; ② Diagnosed with early pregnancy missed abortion by imaging and laboratory examinations; ③ All indicators of routine examinations before treatment are within the normal range, and there are no serious systemic diseases; ④ No indication for emergency curettage ; ⑤ Good compliance, and follow-up observation as required (prospective study).

Exclusion criteria:

① Those with contraindications to medical abortion; ② Those allergic to estrogen or with contraindications to estrogen use; ③ Those unable to follow up according to the follow-up plan; ④ Those with thromboembolic diseases, known or suspected breast cancer, hormone-dependent tumors, etc.; ⑤ Those with vaginal bleeding exceeding the

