For all patients with missed abortions, treatment to promote uterine contraction after the expulsion of the pregnancy tissue includes: routine intravenous administration of uterotonic agents (oxytocin is commonly used , and ergonovine may be used if

necessary) ; and oral administration of uterotonic drugs (such as Wujia Shenghua capsules) for 2 weeks. Infection prevention: If signs of infection or high-risk factors for infection are present, antibiotics may be used as appropriate, and the type, route of administration, dosage, frequency, and duration of administration of antibiotics must be accurately recorded. Pathological examination: The pregnancy tissue expelled during the procedure is routinely sent for pathological examination; chromosomal analysis of the abortion tissue is performed based on the patient's preference.

End of treatment sign:

(1) A follow-up ultrasound showed no retained products of conception, and serum HCG levels returned to normal; (2) Patients with retained products of conception underwent clinical observation or curettage.

5. Key Evaluation Indicators

(1) Evaluation indicators before treatment: patient's age, time of consultation, gestational week of termination of pregnancy, symptoms, ultrasound findings of uterine size, gestational sac size and location, serum HCG level, parity , number of previous intrauterine procedures, and whether there are other intrauterine diseases before pregnancy (such as intrauterine adhesions, uterine septum , submucosal fibroids).

(2) Routine examination data after admission: routine vaginal discharge test, HPV/TCT, routine blood tests, liver and kidney function tests, electrolyte test , coagulation function test, thyroid function test, blood β -HCG test, anti-Müllerian hormone test, pre-transfusion examination, electrocardiogram, chest X-ray, uterine and bilateral adnexa 2-D/3-D color Doppler ultrasound and other related examinations.

(3) During drug treatment: the type and dosage of drugs taken, the time of expulsion of the gestational sac, the amount of vaginal bleeding, adverse drug reactions, etc.

(4) Surgical data: Date of surgery; depth of uterus; location and size of the gestational tract; operation time (from the start of the distension procedure to the withdrawal of the endoscope); amount of intraoperative blood loss; whether there is any retained gestational tract after surgery; clarity of the intraoperative field of vision;

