volume of distension fluid in and out; whether there is a decrease in blood oxygen saturation; whether complications such as uterine perforation, acute left heart failure, or gas embolism occur. Postoperative follow-up data : serum β -HCG, complete blood count, CRP, procalcitonin (not necessary), ultrasound to check for retained gestational tract, and if so, record the maximum diameter of the retained tract.

(5) Outpatient follow-up data 3 months after treatment : duration of vaginal bleeding after miscarriage, amount of bleeding, time of menstruation resumption , changes in menstrual flow , whether ultrasound indicates intrauterine adhesions, condition of endometrium, whether intrauterine adhesion surgery was performed, and intrauterine adhesion score.

(6) Pregnancy outcomes: Pregnancy rate after 1 year of trying to conceive (followed up every 6 months) ; spontaneous abortion rate, premature birth rate, full-term birth rate, stillbirth rate in subsequent pregnancies.

Follow-up data is used only for clinical efficacy evaluation.

6. Safety considerations

The data in this study are derived from clinical data and are absolutely safe. The use of estrogen for missed abortion is in accordance with routine clinical treatment, with the standard dose being 2 mg. 4 mg of estrogen is an off-standard dose, but numerous domestic and international studies have shown that high-dose estrogen for women of childbearing age without contraindications to estrogen use can effectively improve patients' clinical symptoms and has a high safety profile.

7. Statistical Analysis

using SPSS 26.0 software. Normally distributed measurement data were expressed as ($\bar{x} \pm s$), and t-tests were used for comparisons between two groups, while ANOVA was used for comparisons among multiple groups. Non- normally distributed measurement data were expressed as the median, and a nonparametric rank-sum test was used . Categorical data were analyzed using the χ^2 test or Fisher 's test. $P < 0.05$ was considered statistically significant.

8. Data integrity and quality assurance

Researchers should ensure that data is authentic, accurate, complete, and traceable, and should ensure the integrity of basic clinical research documents during retention, avoiding intentional or unintentional alteration or loss.

9. Ethical Statement

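### Efficacy is the stated aim, but no primary outcome is named, and complete evacuation is not recorded with one criterion and time point in both treatment groups

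*Protocol*

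**What the plan says.** Protocol Section 2 states the purpose: "This study aims to collect clinical data on this type of disease to compare the differences in efficacy of different treatments". Section 4 gives Part I the task to "explore the differences in efficacy and fertility outcomes among patients with different treatment methods for missed abortion". No indicator is called primary or main for either part.

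Section 5 lists what is recorded:

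- **5(3), drug treatment:** "During drug treatment: the type and dosage of drugs taken, the time of expulsion of the gestational sac, the amount of vaginal bleeding", then adverse reactions and an open-ended 'etc.'
- **5(4), surgical data:** among the operative items, "whether there is any retained gestational tract after surgery". The postoperative follow-up in the same item adds serum β-HCG and "ultrasound to check for retained gestational tract, and if so, record the maximum diameter of the retained tract".
- **5(5) and 5(6):** the 3-month outpatient data and the pregnancy outcomes, not split by treatment. The line after them assigns follow-up data to the evaluation of clinical efficacy.

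The end-of-treatment sign, just before Section 5, applies to all patients and has two branches. The first is a clear ultrasound with HCG back to normal. The second reads "Patients with retained products of conception underwent clinical observation or curettage". Neither branch has a time point.

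Section 7 gives one general threshold, under which P < 0.05 "was considered statistically significant".

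**The concern.** The most direct meaning of efficacy here is whether the uterus was emptied without a further procedure. The Background makes that the case for drug treatment: if the tissue is fully expelled, curettage is avoided. Yet Section 5 lists neither complete evacuation nor a later or repeat evacuation. What it does list for the treatment phase differs by treatment: time of sac expulsion for drug, retained tissue for surgery.

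Sac expulsion and an empty uterus are different events. The drug pathway in Section 4 itself describes partial expulsion with tissue remaining, and patients who go on to hysteroscopic surgery. Nothing says how such patients count.

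Two things are at stake. The drug v surgery comparison may have no treatment-success measure that means the same in both groups. And with no primary outcome, any one of the indicators common to both groups could be presented as the efficacy result after the data are seen.

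**Working it through.** **1. Is evacuation recorded alike in both groups?** The Section 5 lists and the end-of-treatment sign, side by side:

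| Item | Drug, 5(3) | Surgery, 5(4) | Both groups |
|---|---|---|---|
| Time of sac expulsion | listed | not listed | no |
| Retained tissue | not listed | listed | only in the end-of-treatment sign |
| Ultrasound check and diameter of retained tissue | not listed | listed | clear scan only in the end-of-treatment sign |
| HCG after treatment | not listed | listed | only in the end-of-treatment sign |
| Later or repeat evacuation | not listed | not listed | not in 5(5), which asks only about adhesion surgery |

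**2. Can the end-of-treatment sign serve as the outcome?** Not as written. It is not listed as an indicator and has no time point. Both cleared and retained cases meet it, so reaching it does not mean success. Its branches do describe different states, so an outcome can be built from them once a time is fixed.

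**3. Does the Section 4 drug pathway fill the gap?** In part. Partial expulsion brings weekly β-HCG and ultrasound every 2-3 weeks. The heavy-bleeding branch brings weekly β-HCG and ultrasound at 3-4 weeks. The branch for complete expulsion sets no ultrasound or HCG date. Timing therefore depends on how the patient is doing, and no common assessment time follows.

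**4. What is common to both groups?**

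- 5(5): bleeding duration, bleeding amount, return of menses, menstrual flow, adhesions on ultrasound, endometrium, adhesion surgery, adhesion score = 8.
- 5(6): pregnancy rate, spontaneous abortion, premature birth, full-term birth, stillbirth = 5.
- Total: 8 + 5 = 13.

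**5. False-positive risk if each of the 13 were tested at 0.05 and none were primary** (two-sided tests, no true difference on any of them):

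- Independent: 1 − 0.95^13 = 1 − 0.513 = 0.487, about 49%.
- Equal correlation 0.3 between test statistics (assumed): about 42%.
- Equal correlation 0.5 (assumed): about 33%.

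The correlated figures come from the joint normal distribution of 13 equally correlated statistics. The protocol gives no correlations.

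**6. The plan's own figures.** Section 3 states 400 and 180 cases with no outcome, effect or power, so there is nothing to reproduce.

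**The case against.** The strongest reply is that efficacy outcomes common to both groups do exist. Items 5(5) and 5(6) are not split by treatment, and the protocol assigns follow-up data to efficacy evaluation. This stands. A reader might infer that no efficacy outcome is recorded alike, so drug and surgery cannot be compared at all; the document does not support that. The gap concerns treatment success and the missing primary outcome.

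A reader might also infer that drug success will be read from sac expulsion and surgical success from residual tissue, which would favour drug treatment. The protocol nowhere makes expulsion a success criterion. It records the time of expulsion, in an open-ended list. The heading of 5(4) is surgical data, which could also cover drug patients who later have surgery. Retained tissue is looked for in some drug branches. The direction and size of any bias therefore cannot be derived. Setting an assumed rate of retained tissue against the cited background rates of 81% and 96% would only return the assumption.

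Third, handling of multiple tests is commonly left to a SAP, and Section 7 states a general threshold, not a plan to test every indicator. That is fair, so the 33-49% is conditional. Counting every item in Section 5 would overstate it, because surgery-only items such as operation time cannot yield a drug v surgery finding. Naming the main outcome and the data to be collected for it remains a protocol matter.

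**Conclusion.** The point holds in this form. The protocol aims "to compare the differences in efficacy of different treatments" but names no primary outcome, and complete evacuation has no single criterion and time point across the two groups. Retained tissue, its ultrasound check and HCG after treatment are indicators for surgery only. Later evacuation is an indicator for neither. These statements rest on the text alone.

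The size attaches to the missing primary outcome: about a 49% chance of at least one false positive over the 13 common indicators if independent, and about 33-42% with correlation 0.5-0.3. It assumes that each is tested at 0.05 without adjustment and that there is no true difference. No size or direction can be given for bias in the drug v surgery comparison. The gap should be closed, and it does not make the comparison impossible.

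**What to change.** In Section 5:

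1. Name one primary outcome for drug v surgery. An example is complete evacuation (no retained products on ultrasound and HCG back to normal) without unplanned or repeat evacuation, judged at one fixed time counted from start of treatment in both groups.
2. Add two fields to the drug-group record: retained products, and later evacuation with its date. Record any repeat evacuation after surgery in the same way.
3. State how patients count. Those with retained products at the fixed time, or with an unplanned or repeat evacuation before it, are not successes. Those who clear under observation alone by then are successes, so entering the second branch of the end-of-treatment sign is not by itself a failure.
4. Label all other indicators secondary or exploratory and report them with confidence intervals.

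This defines how results are scored and leaves patient management unchanged.

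The cost is protocol wording and two data fields. Fewer results can be called confirmatory. In Part I new fields cannot create data: the protocol gives no follow-up schedule for the 2018-2023 patients, so the outcome depends on what their records hold. Report the number with missing ultrasound or HCG by group. In Part II the complete-expulsion branch sets no ultrasound or HCG date, so the sponsor should confirm that routine care supplies both near the chosen time.

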The retrospective analysis included patients diagnosed with missed abortion by ultrasound at our outpatient clinic from January 2018 to March 2023. Patients meeting both inclusion and exclusion criteria were consecutively enrolled. The prospective study included patients diagnosed with missed abortion by ultrasound at our outpatient clinic from December 2023 to December 2024. Patients meeting both inclusion and exclusion criteria were consecutively enrolled. General information was collected from patients in different groups, including gestational age at termination of pregnancy, symptoms, ultrasound findings of uterine size, gestational

sac size and location, serum HCG levels, parity, and whether there were other intrauterine diseases before pregnancy. Patients were grouped according to their wishes and underwent either drug or surgical treatment. Surgical time, intraoperative blood loss, type and dosage of medications, time of gestational sac expulsion, amount of vaginal bleeding, and adverse drug reactions were recorded. Follow-up included the duration and amount of vaginal bleeding after discharge, time of menstrual resumption, changes in menstrual flow, and the probability and outcome of subsequent pregnancies.

Selection criteria:

1. Retrospective analysis : Patients diagnosed with missed abortion by ultrasound at our outpatient clinic from January 2018 to March 2023 who met the inclusion criteria but did not meet the exclusion criteria were enrolled consecutively.

2. Prospective study: Patients diagnosed with missed abortion by ultrasound at our outpatient clinic from December 2023 to December 2024 who met the inclusion criteria but did not meet the exclusion criteria were enrolled consecutively.

Inclusion criteria:

① Age 18-40 years ; ② Diagnosed with early pregnancy missed abortion by imaging and laboratory examinations; ③ All indicators of routine examinations before treatment are within the normal range, and there are no serious systemic diseases; ④ No indication for emergency curettage ; ⑤ Good compliance, and follow-up observation as required (prospective study).

Exclusion criteria:

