misoprostol is not expelled after medical abortion but there is no heavy vaginal bleeding, continue to administer 400µg of misoprostol sublingually or vaginally 3 hours later . The total daily dose (misoprostol) should not exceed 1800µg . If the misoprostol is still not expelled, surgical treatment may be temporarily withheld on the second day. High-dose estrogen 2mg B id can be combined to improve uterine contraction sensitivity. If the misoprostol is still not expelled, observation for one week or hysteroscopic surgery can be chosen.

③ If part of the pregnancy tissue is expelled without heavy bleeding and vaginal bleeding is less than menstrual flow, surgery may not be necessary initially. For those without contraindications, administer 2mg of estradiol valerate twice daily, check β-HCG weekly, and have a follow-up ultrasound every 2-3 weeks. If, during the waiting period, the pregnancy tissue is expelled and the remaining tissue is less than 5 mm in diameter , an artificial cycle will be initiated . After the next menstrual period, a follow-up ultrasound and HCG test will be performed, and the doctor will assess whether further surgery is needed. If heavy bleeding (more than twice the menstrual flow) occurs during the treatment, emergency hospitalization is required . If infection occurs during the treatment, emergency hospitalization is required, followed by aggressive anti-infection treatment and, depending on the circumstances, a curettage procedure may be necessary.

④ Heavy bleeding during medical abortion, with intensified uterine contractions (such as oxytocin) failing to expel the pregnancy tissue, and excessive bleeding. Examination reveals the pregnancy tissue is still within the uterine cavity, especially with no tissue impaction in the cervical canal (if present, it should be immediately removed with ovum forceps) . If bleeding significantly decreases after ovum forceps clamping , surgery is not performed immediately; instead, uterine contractions are intensified, and β-HCG is checked weekly. A follow-up ultrasound is performed in 3-4 weeks. If vaginal bleeding remains heavier than menstrual flow after clamping, emergency hysteroscopic-assisted or direct hysteroscopic surgery is necessary.

(2) Surgical treatment group: Patients clinically diagnosed with early pregnancy loss and choosing surgical treatment were grouped according to their own wishes. Group G

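### Section 5 defines no complication outcome common to drug and surgical patients, and it does not name infection, emergency admission or unplanned evacuation after drug treatment, which the protocol itself foresees

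*Protocol*

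**What the plan says.** Section 2 (Research Objectives) states that the study will "evaluate whether the treatment plan achieves the desired therapeutic effect while reducing the occurrence of complications". In that section the phrase follows directly on combining estrogen doses with medical induction. The end of section 1 ties the same aim to mifepristone, misoprostol and high-dose estrogen.

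Section 5 then lists what is recorded:

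- Item (3), during drug treatment: drugs and doses, then "the time of expulsion of the gestational sac, the amount of vaginal bleeding, adverse drug reactions, etc".
- Item (4), surgical data: operative details and "whether complications such as uterine perforation, acute left heart failure, or gas embolism occur". The postoperative items include blood count, CRP, procalcitonin (marked as optional) and an ultrasound for retained tissue.
- Item (5), the 3-month outpatient visit, not restricted by treatment: bleeding duration and amount, menstrual changes, intrauterine adhesions, adhesion surgery and adhesion score.

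The management text for drug patients in the prospective study (section 4, Treatment methods, Drug treatment group) foresees three emergencies. On bleeding: "If heavy bleeding (more than twice the menstrual flow) occurs during the treatment, emergency hospitalization is required". On infection: "If infection occurs during the treatment, emergency hospitalization is required, followed by aggressive anti-infection treatment", with curettage as a possible next step. The third is emergency hysteroscopic surgery when bleeding stays heavy after tissue has been removed from the cervix.

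**The concern.** A study that asks whether a regimen reduces complications has to count the same events, in the same way, in every group compared. Here the only item labelled *complications* gives operative examples, which a drug patient can have only if she goes on to surgery. The harms that the protocol expects of drug treatment appear as management instructions, not as things to be recorded and compared.

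Two comparisons are affected. Between drug and surgery, ascertainment differs by treatment, in a study where patients choose their own treatment. Among the estrogen-dose groups within drug treatment, the list is at least the same for all, but it leaves out events that would show whether the regimen does reduce complications. The case for drug treatment in section 1 includes avoiding curettage when expulsion is complete, yet whether curettage was avoided is not an indicator.

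**Working it through.** No arithmetic applies. The check matches each event that the protocol foresees or calls a complication against section 5.

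| Event | Where the protocol raises it | Section 5, drug patients | Section 5, surgical patients |
|---|---|---|---|
| Heavy bleeding with emergency admission | Section 4, drug group | Amount in (3) and (5); admission not named | Operative loss in (4), amount in (5); admission not named |
| Infection | Section 4, drug group; section 1 for surgery | Not named | Not named; blood count, CRP and procalcitonin in (4) |
| Unplanned, emergency or repeat evacuation | Section 4, drug group | Not named as an event | Not named as an event |
| Retained tissue on ultrasound | Section 4, drug group and end-of-treatment sign | Not an indicator | In (4) |
| Cervical injury | Section 1, for surgery | Not named | Not named |
| Perforation and similar operative events | Section 1 (perforation) and item (4) | Only if she is operated on | In (4) |
| Adverse drug reactions | Summary and item (3) | In (3) | Not listed |
| Intrauterine adhesions | Section 1 | In (5) | In (5) |

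Reading across the rows:

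1. Of the three emergencies foreseen in drug patients, none is named as an indicator. Heavy bleeding is partly covered, because its amount is recorded. Infection and emergency surgery are not.
2. The harms recorded in both groups are bleeding and intrauterine adhesions, with adhesion surgery and score.
3. Infection markers and the retained-tissue ultrasound are indicators on the surgical side only.
4. Infection and cervical injury are unnamed on the surgical side as well, so the omissions do not all fall on one treatment.

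The Summary does not fill the gap. For drug patients it repeats "time of gestational sac expulsion, amount of vaginal bleeding, and adverse drug reactions were recorded". Outside section 5, the paragraph on care for all patients requires antibiotic details to be recorded. It allows antibiotics for risk factors as well as for signs of infection, so that record alone is not an infection outcome.

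**The case against.** The strongest reply has five parts.

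**Complications are covered elsewhere.** Item (5) applies to everyone, and section 1 itself treats adhesions and menstrual disorders as complications. Item (3) adds bleeding and adverse reactions. This stands. A reader might infer that complications are listed only as operative events, or that the drug group's complication rate would come out near zero. The document supports neither reading, because a drug patient can have several of the listed harms.

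**The lists are open, and item (4) is headed Surgical data.** Its heading is not limited to the surgical treatment group, so a drug patient who is later operated on may have her operation recorded there. This is a fair reading and partly stands. But an open ending does not secure uniform recording, and the protocol does not say to which group such an operative event counts.

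**No complication rate between drug and surgery is specified.** The aim attaches most directly to medical abortion with estrogen, and Part I is described in terms of efficacy and fertility outcomes. This is right, and it limits any claim of a tilted comparison. It does not remove the gap, because the unnamed events are the foreseen harms of that very regimen.

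**Different tests follow from routine care.** Section 4 says that the study adds no examinations. This stands for blood tests. It does not explain why admissions, treated infections and evacuations, which routine records should contain, are not indicators.

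**The details could sit in an analysis plan.** The definition of a composite and its analysis could. Section 4 describes the study as one that designs in advance what is collected, and section 5 is that design. An analysis plan cannot recover events that were not uniformly recorded.

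**Conclusion.** The point holds in a limited form. Section 5 has no complication outcome common to both treatments, and it does not name infection, emergency admission for bleeding, or unplanned evacuation after drug treatment, although section 4 foresees them. The gap is partial, because bleeding, adverse drug reactions and adhesions are covered. It should be closed, but it does not invalidate the study.

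No figure can be put on the effect. A reader might multiply the effectiveness figures in section 1 (81% for drug treatment, 96% for surgery) by an assumed split of the 180 prospective patients and conclude that a shared list would reverse the comparison. That does not follow. Those are effectiveness figures, not complication rates; patients choose their treatment, so the split is unknown; and events are unnamed on both sides. The direction of any bias is therefore open.

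The conclusion assumes that data collection follows section 5 as written. If a case report form already captures these events in both groups, only the protocol wording needs to change.

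**What to change.** Add to section 5 one complication list, applied identically to drug and surgical patients in both parts and completed from existing hospital records, covering the time from first drug dose or procedure to the 3-month visit:

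- infection treated with antibiotics, separating therapeutic from prophylactic use, with the antibiotic record that section 4 already requires as the source;
- emergency admission for bleeding;
- unplanned or repeat uterine evacuation;
- cervical injury or perforation;
- other operative events.

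Attribute every event to the treatment first chosen, including events during surgery after failed drug treatment. Keep the existing items on bleeding, adverse drug reactions and adhesions. The sentence closing section 5, which reserves follow-up data for efficacy evaluation, needs a matching edit.

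The cost is a change of wording and a short extra record abstraction, with no added test and no change to treatment. For the retrospective part, the list can be only as complete as the records. Complication figures may look less favourable than under the present list.
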